Study Title

TEE Image Quality Improvement With Our Devised Transesophageal Echocardiography Probe Cover and Its Effect on Surgical Decision Making

NCT03812185

Date: 01/18/2019

Study Design

This study was designed as a two-point evaluation at a single tertiary care medical center. This study was approved by the Henry Ford Health System Institutional Review Board (IRB #11958), and written consent was obtained from patients before enrollment. Additionally, this study was registered at ClinicalTrial.gov (NCT 03812185). This was a prospective, observational study of a cohort of adult patients who underwent surgeries requiring intraoperative TEE between January 2019 and December 2019 at Henry Ford Hospital in Detroit, MI. TEE data were collected from intraoperative TEE images as part of a prospective echocardiographic protocol using 2-dimensional (2D) TEE views. The demographics, perioperative clinical information, and postoperative outcomes of these patients were collected from our computerized patient database.

Patient Cohort

Adult patients undergoing surgeries requiring intraoperative TEE between January 2019 and December 2019 were included. The exclusion criteria were patient refusal to participate in the study, absolute contraindication to TEE, significant wall motion abnormality that hindered measurement of the left ventricular fraction area change (LV FAC), and inability to advance the OG tube through the TEE probe cover. All patients received general anesthesia with endotracheal intubation, standard American Society of Anesthesiologists monitoring, arterial blood pressure monitoring, central venous pressure monitoring, pulmonary artery pressure monitoring, and a comprehensive TEE examination with a designated protocol. Intraoperative management with anesthetics, mechanical ventilation, vasopressors, inotropic agents, and fluids/transfusions was performed based on department protocols, such as maintaining a mean arterial pressure > 65 mmHg, tidal volume 6-8 ml/ideal body weight (kg), and positive end-expiratory pressure 5-7 cmH2O.

Data Collection

After general anesthesia induction, our newly designed TEE probe cover (FIGURE 1; Fuji Medical, Tokyo, Japan) was attached to the X7 TEE probe (Philips Medical Systems, Andover, MA) and inserted into the patient's esophagus, and an OG tube (Salem Sump nasogastric tube, 16 Fr., Covidien, Minneapolis, MN) was advanced through the second lumen of the TEE probe cover. The length of advanced OG tube was adjusted so that the tip of OG tube would be 2-3 cm out of the second lumen. TEE images were intraoperatively collected by National Board of Echocardiography (NBE)-certified advanced

perioperative echocardiographers, who are blinded to this study design, using an iE33 echocardiographic machine (Philips Medical Systems, Andover, MA) and stored in Syngo Workflow (Siemens Medical Solution, Malvern, PA, USA). The designated views for TEE images were as follows: midesophageal 4-chamber view (ME4C), midesophageal 2-chamber view (ME2C), midesophageal aortic valve short-axis view (ME AV SAX), midesophageal long-axis view (ME LAX), midesophageal bicaval view (ME BIC), transgastric midpapillary short-axis view (TG Mid SAX), and deep transgastric long-axis view (DTG LAX). Image acquisition was performed twice, before and after OG tube suctioning, when the baseline TEE assessment was performed after general anesthesia induction. Suction was performed for 1 minute at > -110 cm H₂O, and the amount and characteristics of the suctioned content were recorded. While acquiring these views, the TEE device setting was not changed, and the iSCAN button was pressed before video acquisition.¹⁰⁻¹³

Image quality assessment

TEE image quality was assessed in 2 different ways based on the TEE images acquired before and after suctioning. In the first method (method #1), the investigators categorized the quality of all acquired images on a numeric scale based on each investigator's impression (1: very poor, 2: poor, 3: acceptable, 4: good, and 5: very good). In the second method (method #2), the reproducibility of the LV FAC and right ventricular fraction area change (RV FAC) was assessed, assuming that better TG Mid SAX and ME4C image quality would yield better LV FAC and RV FAC reproducibility, respectively.¹⁸ LV FAC was calculated using TG Mid SAX, while RV FAC was calculated using ME4C.

Three investigators (A, B, and C), who were also NBE-certified advanced perioperative echocardiographers, assessed the quality of all TEE images post hoc. Thus, 50 x 3 sets of images for each were evaluated to determine the interobserver variability. Subsequently, following an interval of between 6 and 8 months, investigator C again analyzed all images to determine the intraobserver variability. To minimize selection bias, all investigators were blinded to the hypothesis of the study. Additionally, all investigators were blinded to which images were obtained before or after suctioning.

Outcomes

The quality of images obtained before and after pinpoint suctioning with our newly designed TEE probe cover was assessed using the following views: ME4C, ME2C, ME AV SAX, ME LAX, ME BIC, TG Mid SAX, and DTG LAX. As described in method #1, post hoc assessments were performed using image quality

categorized as discrete numbers based on each investigator's impression (1: very poor, 2: poor, 3: acceptable, 4: good, and 5: very good) before and after suctioning. Image quality improvement was defined as an increase in this number. Additionally, as described in method #2, the LV FAC was also assessed post hoc for intraclass correlation coefficient (ICC) analysis. Furthermore, we assessed the occurrence of TEE probe-related complications (postoperative severe sore throat, dysphagia, bloody aspirate from the OG tube) and the suctioned volume.

Statistical Analysis

Continuous variables with a normal distribution are displayed as the mean \pm standard deviation, while those variables with a nonnormal distribution are displayed as the median and interquartile range. Categorical variables are presented as proportions and absolute numbers. For continuous variables, normality was tested using the Kolmogorov-Smirnov test.

The differences between 2 groups were investigated using the chi-square test or Fisher's exact test if any of the expected frequencies were <5 for categorical variables and unpaired and paired Student's ttests or the Mann-Whitney U test for continuous variables. Differences among 3 groups were investigated using Fisher's exact test for categorical variables and one-way ANOVA or the Kruskal-Wallis test for continuous variables.

Intraobserver and interobserver reliability analyses of the LV FAC and RV FAC were performed using the ICC20-22. We obtained consistency ICCs for interobserver variability using all three investigators and absolute-agreement ICCs for intraobserver variability using investigator C, who measured all images twice at an interval between 6 and 8 months. The proportion of cases showing improvement using the numeric scale and the occurrence of TEE probe-related complications (severe sore throat, dysphagia, and bloody aspirate from the OG tube) are also reported for descriptive assessment. The change in image quality according to the numeric scale (method #1) was averaged for the same case, and its association with the suctioned volume was assessed using Pearson's or Spearman's rank correlation test. All statistical analyses were performed with R (version 4.0.2). A p-value of less than 0.05 was considered statistically significant.

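### Failure to pass the OG tube through the study cover is an exclusion, though it is seen only after the cover is inserted; no failure count or complication denominator is planned

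*Combined protocol and SAP*

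**What the plan says.** All references are to the combined protocol and SAP.

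- **Study Design:** "written consent was obtained from patients before enrollment". Postoperative outcomes come from the centre's computerized patient database.
- **Patient Cohort:** four exclusions are listed together. Two, refusal and absolute contraindication to TEE, can be known before the device is used. A third is "inability to advance the OG tube through the TEE probe cover". The remaining one concerns regional function and turns on whether LV FAC can be measured: "significant wall motion abnormality that hindered measurement of the left ventricular fraction area change".
- **Data Collection:** after induction, the cover is fitted to the probe and the probe is inserted. The OG tube then "was advanced through the second lumen of the TEE probe cover". The items recorded at suctioning are the amount and character of the aspirate.
- **Image quality assessment:** "LV FAC was calculated using TG Mid SAX", a view obtained with the probe in place. The only figure resembling a sample size is here: "50 x 3 sets of images for each were evaluated".
- **Outcomes:** besides image quality and FAC reproducibility, "we assessed the occurrence of TEE probe-related complications" (severe sore throat, dysphagia, bloody aspirate), together with the suctioned volume.
- **Statistical Analysis:** the complications "are also reported for descriptive assessment". Categorical variables are given as counts and proportions, with no population named.

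**The concern.** An eligibility criterion should describe the patient before exposure. Failure of the tube to pass describes how the device performed after exposure. Using it as an exclusion has two consequences.

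1. The cover's suction function depends on the tube passing through its second lumen. If failures leave the cohort and are not counted, the cohort shows complete success whatever happened in practice.
2. A patient in whom the tube did not pass still had the covered probe inserted, and could have a severe sore throat or dysphagia. Read with the exclusion, those two proportions would describe only patients in whom the tube passed. This is an inference, because the documents do not state the denominator.

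The wall motion exclusion may raise the same issue. It turns on whether LV FAC could be measured, which may be judged only once the probe is in, but the documents do not say when it is judged.

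Leaving failures out of Methods #1 and #2 is not at issue: without a passed tube there is no suctioning and no after-suction image.

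**Working it through.** **Order of events.** Consent, then induction, then insertion of the covered probe, then advancement of the OG tube, then images before and after suctioning. Failure can be observed only at the fourth step, after consent and exposure. No check of the lumen before insertion is described.

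**Search for a count or denominator.** Data Collection records nothing about failed advancement. Outcomes does not list it. Statistical Analysis asks for the occurrence of complications without naming a population. No exposed or attempted set is defined anywhere.

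**Size.** The plan has no figure on this point to reproduce, so what follows is an illustration.

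Inputs:
- 50 analysed patients, read from the number of image sets under Image quality assessment (an assumption).
- 1 of the 50 has a given complication (assumed): 1/50 = 2.0%, exact (Clopper-Pearson) 95% CI 0.05% to 10.6%.
- f = tube failures and w = wall motion exclusions made after insertion (both assumed, with no overlap).

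Formulas:
- Exposed patients: N = 50 + f + w.
- Lowest complication proportion (no excluded patient had the event): 1/N.
- Highest (every excluded patient had it): (1 + f + w)/N.
- Failure proportion: f/N, taking the tube to have passed in the wall motion exclusions.

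| f | w | N | Lowest | Highest | Failure proportion (exact 95% CI) |
|---|---|---|---|---|---|
| 2 | 0 | 52 | 1/52 = 1.9% | 3/52 = 5.8% | 2/52 = 3.8% (0.5% to 13.2%) |
| 5 | 0 | 55 | 1/55 = 1.8% | 6/55 = 10.9% | 5/55 = 9.1% (3.0% to 20.0%) |
| 2 | 3 | 55 | 1/55 = 1.8% | 6/55 = 10.9% | 2/55 = 3.6% (0.4% to 12.5%) |
| 5 | 3 | 58 | 1/58 = 1.7% | 9/58 = 15.5% | 5/58 = 8.6% (2.9% to 19.0%) |

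The first two rows involve tube failure only. The last two add the wall motion exclusion and apply only if it is judged after insertion.

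In every row the cohort as defined would show 50 of 50 tubes passed and a complication proportion of 2.0%. The proportion among all exposed could be below or above 2.0%.

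**The case against.** The strongest reply is that the harm is narrow and partly inferred. No hypothesis test changes, and the image comparison is unaffected. Bloody aspirate from the OG tube is sensibly assessed only where a tube is in place. What remains is two descriptive complications and a count. Feasibility is not a stated outcome, so asking for a failure proportion adds something the plan did not set out to estimate. A report could list exclusions by reason in any case. The wording on postoperative outcomes under Study Design precedes the exclusions and could be read as covering a wider group.

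The illustration is also weak as evidence. All counts are assumed, and the upper bounds require every excluded patient to have the event. The sampling interval for 1/50 already reaches 10.6%, so three of the four upper bounds are inside it or about 0.3 percentage points above it. Finally, all patients are intubated and no group without the cover is described, so no choice of denominator would allow a sore throat to be attributed to the cover.

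Most of this stands as a limit on weight. It does not remove the point. The plan does not require exclusions to be listed by reason, and such a list would not supply the excluded patients' complications. The sampling interval does not cover selection after exposure. The plan itself chose to assess probe-related complications, so it should say whom the proportions cover. The wall motion part is the least certain, which is why its rows are kept separate.

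**Conclusion.** The concern holds and should be fixed. The exclusion removes failures of the study device after exposure, and the plan neither counts them nor says whether those patients enter the complication proportions.

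The omission is certain from the text. Its effect is not: the size and direction of any bias are unknown, and the ranges above show what is left open without being evidence of material bias. They rest on 50 being the number of analysed patients, on assumed failure and event counts, and, in the last two rows, on the wall motion exclusion acting after insertion. The effect is confined to feasibility and descriptive safety reporting. The image-quality result stands for patients in whom the tube passed and should be described that way.

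**What to change.** - Remove tube-advancement failure from the cohort exclusions and make it a reported outcome.
- Define a device-exposed set: all consented patients in whom the cover was inserted, including any later excluded for wall motion abnormality. State when that exclusion is judged.
- Report the number and proportion of advancement failures in this set, with an exact 95% CI.
- Report severe sore throat and dysphagia on the same set, showing missing follow-up as missing.
- Report bloody aspirate among patients with a passed tube.
- Keep Methods #1 and #2 on patients with both acquisitions who meet the measurement criteria, and say that the image-quality result applies to them.

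The cost is rewording the cohort, outcome and analysis sections, plus one reported line for failures. Outcomes of excluded patients would have to be retrieved from the patient database. The plan describes no follow-up for them, so some may be unavailable. The downside for the sponsor is a failure proportion that may look less favourable than none; the complication proportions could move either way.

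### The 1–5 image score is summarised only by the proportion improved, with no worsened count, and the listed non-normal test ignores the before/after pairing

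*Combined protocol and SAP*

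**What the plan says.** The Study Design section states: "This study was designed as a two-point evaluation". The Data Collection section adds: "Image acquisition was performed twice, before and after OG tube suctioning". Each case therefore supplies its own control.

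Three readers, blinded to whether an image came before or after suctioning, score seven views from 1 to 5. The Outcomes section then says: "Image quality improvement was defined as an increase in this number". It gives no minimum step, and it does not say whether the unit is the rating, the view, the reader or the case.

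The Statistical Analysis section takes up the score in two places:

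- "The proportion of cases showing improvement using the numeric scale" is listed together with probe-related complications, and these "are also reported for descriptive assessment".
- "The change in image quality according to the numeric scale (method #1) was averaged for the same case", and this average is then correlated with suctioned volume. No other use of it is stated.

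For two-group comparisons of continuous variables, the same section lists unpaired and paired t-tests "or the Mann-Whitney U test for continuous variables". For categorical variables it lists chi-square or Fisher's exact test. No test is assigned to the 1–5 score. The display rule is "Categorical variables are presented as proportions and absolute numbers".

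**The concern.** Repeat acquisition and repeat scoring make some scores rise and some fall even when suctioning does nothing. Blinding the readers to time point keeps those movements roughly symmetric, but it does not remove them. A count of rises can be interpreted only beside the count of falls, and the plan does not ask for the falls. The display rule for categorical variables would be met by reporting 20/50 (40%) alone.

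The score is the plan's direct measure of image quality, which is the subject of the study's title. Neither of the other planned analyses replaces it: the correlation with suctioned volume and the reproducibility of the fractional area changes do not estimate the before/after change in the score.

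If the score is judged non-normal or handled as categorical, every listed test treats the before and after scores as independent samples. That discards the main strength of the design.

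**Working it through.** The plan gives no sample-size calculation, effect size or SD, so it has no figure to reproduce. The inputs from the documents are 50 cases (from the count of image sets read), 7 views, 3 readers and a 0.05 significance level, taken here as two-sided. Everything else below is an assumption and is labelled as one.

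**1. Same proportion improved, different worsened counts (hypothetical counts, n = 50).** With u improved and d worsened, net = (u − d)/n and SE = √[((u + d)/n − net²)/n]. The p-value is the exact two-sided sign test on u against d.

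- u = 20, d = 18: net = 2/50 = 0.04; SE = √[(0.76 − 0.0016)/50] = 0.123; 95% CI −0.20 to +0.28; p = 0.87.
- u = 20, d = 5: net = 15/50 = 0.30; SE = √[(0.50 − 0.09)/50] = 0.091; 95% CI 0.12 to 0.48; p = 0.004.
- With u = 20, the sign test gives p = 0.036 at d = 8 and p = 0.061 at d = 9.

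The planned summary is 40% in every row.

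**2. How often a case counts as improved by chance.** Take the rule that the case mean change is above 0. Assume no effect, and let each independent unit change by −1, 0 or +1 with probabilities (1 − A)/2, A and (1 − A)/2. Here A is the exact agreement between the same reader's before and after scores of a view. The documents do not give A. By symmetry, P(improved) = [1 − P(sum = 0)]/2, computed exactly by convolution over k units.

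| Assumed A | 90% | 80% | 60% | 40% |
|---|---|---|---|---|
| All 21 scores independent (k = 21) | 35% | 40% | 43% | 44% |
| Readers' errors shared within a view (k = 7) | 23% | 32% | 38% | 41% |
| All 21 errors move together (k = 1) | 5% | 10% | 20% | 30% |

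At A = 80% that is about 20, 16 or 5 of 50 cases improved by chance, with as many worsened.

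**3. Effect of the missing case-level rule.** This is a separate simulation of 1–5 scores with no true change. The assumed latent SDs are case 0.6, view within case 0.5, acquisition 0.3 and reader 0.3 to 0.7. The share of cases called improved is:

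- any of the 21 ratings up: 98% to 99.9%;
- any view with a rise in the reader median: 76% to 87%;
- case mean change above 0: 46% to 47%;
- at least 4 of 7 views up on the reader mean: 21% to 30%.

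**4. Cost of the unpaired fallback.** Simulated power for n = 50 pairs, two-sided 0.05 and an assumed shift of 0.3 SD:

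| Assumed within-case correlation | 0.3 | 0.5 | 0.7 |
|---|---|---|---|
| Normal scores, Mann-Whitney | 28% | 25% | 20% |
| Normal scores, signed-rank | 41% | 53% | 75% |
| 1–5 ordinal scores, Mann-Whitney | 25% | 23% | 19% |
| 1–5 ordinal scores, signed-rank | 36% | 46% | 63% |

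With no shift and normal scores, Mann-Whitney rejects in 2.1%, 0.8% and 0.05% of datasets, against about 5% for signed-rank.

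**The case against.** The strongest reply concerns the test. The list is generic and must also serve independent groups, for which Mann-Whitney, chi-square and Fisher are correct. A paired t-test is on it, and the before/after images are the obvious paired data. Normal data would go to that test, with power of about 40%, 55% and 77% in the normal-score setting above, and a case mean of up to 21 ratings may be close to normal. Mann-Whitney on paired data is also conservative, so it could miss a benefit but would not create one. All of this stands, and it limits the testing point to the non-normal and categorical routes. It does not remove the point: on those routes no paired test is offered, and the loss of power also appears with ordinal scores.

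On the summary, it can be said that the proportion is labelled descriptive. The signed case average could also be displayed under the rule for continuous variables, and because it follows directly after the proportion in the text it hints at a case-level rule. These are possible readings, but the plan does not commit to them; the average is tied only to the volume correlation. A description that shows rises without falls remains incomplete.

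The chance rates do depend on assumed agreement and error sharing, and they run from 5% to 44%. That width is a reason to report the falls, because the reader cannot otherwise know where in the range the study lies.

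**Conclusion.** The concern holds and should be fixed. The only before/after summary the plan names for the 1–5 score is one-sided, and the same 40% improved is compatible with no net change or with a clear gain. That conclusion follows from the text and does not depend on any assumed value. The illustrative sizes do: the counts in 50 cases are hypothetical, and agreement, error sharing, shift and within-case correlation are assumed.

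The testing point is conditional. If the score is treated as non-normal, Mann-Whitney gives up 13 to 55 percentage points of power on normal scores (41 − 28 and 75 − 20) and 11 to 44 on ordinal scores (36 − 25 and 63 − 19), over correlations of 0.3 to 0.7. The error is towards missing a benefit. The collected data are unaffected, and a sound analysis can be recovered from them.

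**What to change.** - Choose one before/after summary of the score, with the case as the unit and a 95% CI: the mean paired change per case, which the plan already computes, or the net proportion (improved minus worsened).
- Name one paired test that matches it: the paired t-test, with Wilcoxon signed-rank in place of Mann-Whitney if the changes are non-normal, or the exact sign test for the net proportion. Settle on one pairing, because the options can disagree. At 20 improved and 9 worsened, the Wald interval for the net proportion is +2% to +42%, while the sign test gives p = 0.061.
- State the rule that makes a case improved, and report improved, unchanged and worsened counts side by side under that rule.
- Label per-view results descriptive.
- If investigator C's second reading included the 1–5 scores, its rises and falls may be shown as context for rating noise only. It comes 6 to 8 months later and involves no new acquisition, so it may over- or understate the before/after noise.

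The cost is revised outcome and analysis wording and one extra table from scores already collected; no new images are needed. The mean change treats the 1–5 scale as interval, as the plan's own averaging already does. The reported result may look less favourable.

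### Uncorrected Kolmogorov-Smirnov testing at n=50 would pass most mildly to moderately skewed variables as normal, so skewed data would be summarised by mean and SD

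*Combined protocol and SAP*

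**What the plan says.** The Statistical Analysis section sets a display rule: "Continuous variables with a normal distribution are displayed as the mean" with its standard deviation, "while those variables with a nonnormal distribution are displayed as the median and interquartile range". The test that applies the rule follows: "For continuous variables, normality was tested using the Kolmogorov-Smirnov test". The text names no correction for estimated parameters, no reference mean or SD and no R function.

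Suctioned volume is one of the variables concerned. Under Data Collection, "the amount and characteristics of the suctioned content were recorded". The averaged change in image-quality score is later related to volume: "its association with the suctioned volume was assessed using Pearson's or Spearman's rank correlation test". No rule is given for choosing between the two coefficients, or between the t-tests and the Mann-Whitney test.

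The only case count is in the Image quality assessment section: "Thus, 50 x 3 sets of images for each were evaluated to determine the interobserver variability". The significance level is general: "A p-value of less than 0.05 was considered statistically significant".

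**The concern.** The standard Kolmogorov-Smirnov p-value is valid when the reference normal curve is fixed in advance. If the curve is fitted to the same data through their mean and SD, it lies closer to the sample than the table allows for, and the test becomes far too conservative. The plan supplies no outside values for volume or any other patient variable, so the sample's own values would have to be used.

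Without a correction, the plan's rule of medians for non-normal data would often not take effect. A volume that cannot fall below zero may well be right-skewed, and its mean and SD would then describe a typical patient poorly. If the same result also guided the choice of correlation, r could be driven by a few large volumes.

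**Working it through.** The plan states no error rate for the normality test, so there is no figure of its own to reproduce.

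**Inputs**
- n = 50, read from the image-set count; there is no sample-size statement.
- Level 0.05, assumed to apply to the normality test as well.
- Mean and SD taken from the sample, with no correction (assumed; the plan is silent).
- Distribution of volume: not given, so a range of shapes is used.

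**Statistic.** With z_i = (x_i − mean)/SD for the ordered values and Φ the standard normal distribution function,

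D = max over i of { i/n − Φ(z_i), Φ(z_i) − (i−1)/n }.

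**Critical values at n = 50, 5% level**
- Standard table: 0.1884.
- Correct value when mean and SD are estimated (Lilliefors, simulated): 0.1245.
- Ratio: 0.1884/0.1245 = 1.51, so the standard cut-off is about half as large again as it should be.

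**Size.** Of 100,000 normal samples, 16 exceeded 0.1884: 16/100,000 = 0.016%. A separate set of 20,000 gave 0.01%. The nominal figure is 5%.

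**Rejection rates** (20,000 samples per shape; Shapiro-Wilk on 3,000)

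| Assumed shape | KS, uncorrected | Lilliefors | Shapiro-Wilk |
|---|---|---|---|
| Normal | 0.01% | 4.9% | 4.7% |
| Gamma shape 4 (skewness 1) | 1.7% | 41% | 70% |
| Gamma shape 2 (skewness 1.41) | 8.4% | 70% | 95% |
| Lognormal, sigma 0.5 | 11.5% | 71% | 92% |
| Exponential | 37% | 96% | 99.9% |
| Lognormal, sigma 0.75 | 46% | 95% | 99.7% |
| Lognormal, sigma 1 | 80% | 99.6% | 100% |
| 30% zeros plus exponential | 91% | 100% | 100% |
| Gamma shape 0.5 | 94% | 100% | 100% |
| Gamma shape 2, mean 20 mL, rounded to 5 mL | 40% | 98% | 98% |
| Exponential, mean 20 mL, rounded to 5 mL | 64% | 99.6% | 99.9% |
| Lognormal, sigma 1, median 10 mL, rounded to 5 mL | 96% | 100% | 100% |

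The share passed as normal is the complement: 100 − 1.7 = 98.3% for gamma shape 4, 100 − 8.4 = 91.6% for gamma shape 2 and 100 − 37 = 63% for exponential. For the rounded sigma 1 lognormal it is only 100 − 96 = 4%.

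**Sensitivity to n.** For exponential data the uncorrected test rejects 12% at n=30, 23% at n=40, 38% at n=50 and 93% at n=100.

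**Type I error of Pearson's test.** With volume independent of a normally distributed mean change (20,000 samples per shape, n=50), Pearson's test rejected 4.9% (exponential), 4.7% (lognormal, sigma 1) and 5.0% (lognormal, sigma 0.5).

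**If the normality result also picked the correlation.** Take exponential volume, n=50 and a standardised slope of 0.4.
- Linear relation: power is about 72% when the uncorrected test chooses and about 65% when Shapiro-Wilk chooses, a loss of 72 − 65 = 7 points. Scaling the residual differently moves both figures by several points, but the gap stays near 7 to 8.
- Effect that levels off above the median volume: about 41% for Pearson, 53% when the uncorrected test chooses and 66% for Spearman.

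The better coefficient therefore depends on a shape the documents do not give.

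**The case against.** The strongest reply is that the documents do not show misuse. They name neither an R function nor a correction, and silence is not proof that the uncorrected p-value was used. That stands, and it is why the size of the problem is stated conditionally. It does not remove the point, because a reader who follows the text as written would run the uncorrected test.

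A reader might also infer three stronger things, none of which the documents support.

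- *That the test hardly ever rejects skewed data.* This is true for normal and mildly skewed data only. Strong skew, many zeros or coarse rounding of exponential volumes raise rejection to about 64-96%. How often volume itself would be misclassified is unknown.
- *That the test sends volume to Pearson.* The only written consequence of normality is the display rule. No basis for Pearson or Spearman is stated.
- *That the volume association would produce too many false positives.* Pearson's type I error stayed at 4.7-5.0% under independence.

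It is also fair to say that the consequence is small. Volume is a supplementary outcome, and the ICC analyses and improvement proportions do not depend on this test.

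**Conclusion.** The concern holds as a minor but concrete weakness in the choice of method. If the Kolmogorov-Smirnov test is run with the sample mean and SD and no correction, its size at n=50 is about 0.01-0.02% instead of 5%. It then misses roughly 60% of unrounded exponential samples and over 85% of milder skewed ones (gamma shapes 4 and 2, lognormal sigma 0.5). Skewed variables of that kind would be shown as mean and SD, against the plan's own rule. Any effect on the choice of correlation test is only a possibility.

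The conclusion assumes 50 cases, a 5% level for the normality test and the shapes shown. It lapses if a Lilliefors correction was in fact used, in which case the text should say so.

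**What to change.** Replace the Kolmogorov-Smirnov test with Shapiro-Wilk for all continuous variables, or state that Lilliefors-corrected p-values are used. Both restore a size near 5%; Shapiro-Wilk detects the milder skew more often (70% against 41% for gamma shape 4). If summaries have already been produced, rerun the check and change to median and IQR where the result differs.

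The cost is one sentence and one base R function. The change is not wholly free: if the normality result also picks the correlation and the relation with volume is truly linear, power falls from about 72% to 65% in the scenario above. The plan should therefore also state how Pearson or Spearman is chosen.

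Reporting both coefficients with a scatterplot is a sensible option. Fixing Spearman alone is a trade-off that depends on an unknown shape, and it is not part of the required change.
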